14.0 STATISTICAL CONSIDERATIONS

14.1 General Considerations

This is an open-label, single-arm, phase II trial of Rituximab in combination with Acalabrutinib treating newly diagnosed B cell post-transplant lymphoproliferative disorder. The primary objective is to assess the efficacy of the combination regimen. The primary endpoint is overall response rate (ORR) 8 weeks after treatment completion. Secondary endpoints include complete response rate (CRR), partial response rate (PRR), duration of response (DoR), overall survival (OS), progression-free survival (PFS), time to treatment failure (TTF) and toxicity profile.

14.2 Rational for Sample Size

The null ORR of single agent Rituximab is 60% based on literature ⁶⁻¹¹. We expect the ORR (CR +PR) of combination regimen be at least 75%. Using one-sample exact binomial test, 62 patients will ensure a power of 80% at two-sided type I error rate of 10% to detect such a difference. The trial will be considered a success if 44 or more CRs/PRs are observed out of 62 patients.

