14.3 Futility Monitoring Rule

We expect the ORR of Rituximab + Acalabrutinib will be 15% or higher than Rituximab alone. We will monitor the ORR and stop the trial early for futility if observed ORR is unlikely to achieve the target (75%). A Bayesian method ³¹ will be used to monitor futility. The reference ORR was assumed to follow a Beta(60,40) distribution, which corresponds to an expected ORR of 60% with an effective sample size of 100. The prior distribution of true ORR was set as Beta(0.6,0.4), which also has an expected ORR of 60%, but with an effective sample size of 1. Futility monitoring will start from the 10th patient and in cohorts of 10 thereafter. We will stop the trial early if $\text{Pr}(\text{ORR} < 0.60 + 0.15 | \text{data}) > 0.9$, i.e. stop the trial early if the posterior probability of experimental ORR missing target (75%) is high (>0.9) given data. Table 5 summarizes early stopping boundaries, and table 6 summarizes operating characteristics.

Table 5. Summary of futility stopping boundaries using Bayesian monitoring rule. Futility monitoring will start from the 10th patient and in cohorts of 10. Trial will stop early if the number of CRs/PRs observed is less than or equal to the boundaries. For example, if we observed 5 or less CRs/PRs out of the first 10 patients, we will stop the trial early. Similarly, if we observed less than or equal to 12/20, 18/30, 25/40, or 32/50 CRs/PRs, we will stop the trial early for futility.

Total Number of Patients Treated	10	20	30	40	50
Number of CRs/PRs Observed <=	5	12	18	25	32

Table 6. Summary of operating characteristics based on 10,000 simulations using early stopping boundaries in table 5. E.g. If the true ORR is 75%, the early stopping probability is 0.17; if the true ORR is 60% (same as Rituximab alone), the early stopping probability is 0.84; if the true ORR is 50% (worse than Rituximab alone), the trial will stop early with probability 0.99. MultcLean v2.1 from MDACC was used to calculate the stopping boundaries and operation characteristics

Scenario	True ORR	Pr(Early Stopping)	Average #Patients Enrolled	Average #CR/PR Observed
1	0.80	0.06	57.5	46.0
2	0.75	0.17	53.0	39.8
3	0.60	0.84	26.9	16.1
4	0.50	0.99	15.9	7.9

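### The stated 80% power ignores the mandatory futility rule; the design as written has about 74% power at the 75% target response rate

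*Combined protocol and SAP*

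**What the plan says.** Section 14.2 sets the null at 60% ("The null ORR of single agent Rituximab is 60% based on literature") and the target at 75%. It uses a one-sample exact binomial test and states that "62 patients will ensure a power of 80% at two-sided type I error rate of 10% to detect such a difference". The decision rule is: "The trial will be considered a success if 44 or more CRs/PRs are observed out of 62 patients". Interim stopping is not mentioned.

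Section 14.3 adds a Bayesian futility rule: "Futility monitoring will start from the 10th patient and in cohorts of 10 thereafter". Table 5 gives the boundaries as 5/10, 12/20, 18/30, 25/40 and 32/50. The wording is mandatory: "Trial will stop early if the number of CRs/PRs observed is less than or equal to the boundaries". Nothing allows the trial to continue past a boundary. The section also reports: "If the true ORR is 75%, the early stopping probability is 0.17". Table 6 lists the stopping probability, average enrolment and average number of responses for four true ORRs. It does not list the probability that the trial succeeds.

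**The concern.** The 80% in section 14.2 belongs to a trial that always reaches 62 patients. Under section 14.3, about one trial in six does not get there even when the regimen performs exactly at target. Some of those stopped trials would have gone on to 44 responses, so they are lost successes. Power for the trial as designed must be below the single-stage figure, and no section says by how much.

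Power is the stated justification for enrolling 62 patients. Anyone approving the trial, or later interpreting a stopped or negative result, would take the false-negative risk at the target to be 20%.

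**Working it through.** **Inputs.** From section 14.2: p0 = 0.60, p1 = 0.75, N = 62, success at X ≥ 44. From section 14.3, Table 5: stop if responses are ≤ 5, 12, 18, 25 or 32 after 10, 20, 30, 40 or 50 patients.

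**Step 1: reproduce the plan's figure (no looks).** With X ~ Binomial(62, p):

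- P(X ≥ 44 | p = 0.60) = 0.0492, within the 5% upper tail of a two-sided 10% test.
- P(X ≥ 44 | p = 0.75) = 0.812, which agrees with the stated 80%.
- 44 is the right cut-off. A cut-off of 43 gives an upper-tail error of 0.083, and 45 gives power of 0.726.

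**Step 2: add the futility looks.** Let f_m(k) be the probability of having k responses after m patients without having stopped. Start from f_0(0) = 1 and repeat for m = 10, 20, 30, 40, 50 with boundaries b_m:

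- f_m(k) = Σ_j f_(m−10)(j) × P(Binomial(10, p) = k − j)
- P(stop at m) = Σ f_m(k) over k ≤ b_m; those states are then set to zero.

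Finally, P(success) = Σ_k f_50(k) × P(Binomial(12, p) ≥ 44 − k).

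**Step 3: check against Table 6.**

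| True ORR | P(stop), Table 6 | P(stop), recomputed | P(success), with looks |
|---|---|---|---|
| 0.80 | 0.06 | 0.058 | 0.925 |
| 0.75 | 0.17 | 0.173 | **0.739** |
| 0.60 | 0.84 | 0.844 | **0.040** |
| 0.50 | 0.99 | 0.990 | 0.0005 |

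The stopping probabilities match at all four ORRs, so this is the plan's own rule. A simulation of 400,000 trials at 0.75 gave 0.738 for success.

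**Step 4: where the power goes at ORR 0.75.** A lost success is a stopped trial that would have reached 44/62 had it continued.

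| Look | P(stop) | Lost successes |
|---|---|---|
| 10 | 0.078 | 0.042 |
| 20 | 0.059 | 0.027 |
| 30 | 0.011 | 0.003 |
| 40 | 0.014 | 0.002 |
| 50 | 0.012 | < 0.001 |
| Total | 0.173 | 0.074 |

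The total closes the account to rounding: 0.812 − 0.074 ≈ 0.739. The looks at 10 and 20 account for 0.042 + 0.027 = 0.069 of the 0.074.

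**Step 5: sensitivity to the boundaries.** If the stopping formula in section 14.3 is applied with a fixed 75% target, the boundaries become 5, 12, 19, 26 and 33, and power falls to 0.720. A further look at 60 patients would change nothing: stopping at 40 or fewer of 60 removes only trials that could end with at most 42 of 62.

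**The case against.** The strongest reply is that section 14.2 contains no miscalculation. It ties the 80% to a named test, and for that test the figure is correct and slightly conservative. The 17% stopping risk is disclosed in the next section, in prose and in Table 6. Type I error is not inflated; it falls from 4.9% to 4.0%. If the true ORR is 80%, power is still 92.5%.

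All of that is true, but it does not rescue the claim. The sentence says what 62 patients will ensure, and the trial so described includes mandatory stopping. The 17% tells a reader only that power is at most 83%, which looks compatible with 80%. About 57% of the stopped trials (0.099 of 0.173) would have missed 44 anyway, so the real figure cannot be worked out from the stopping probability alone.

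One could also argue that the rule is advisory. If every boundary were overruled, power would return to 81.2%. The text does not say this, and Table 6 would then no longer describe the trial.

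One qualification stands. The primary endpoint is read 8 weeks after treatment completion (section 14.1), after as many as four cycles (section 3.4). Section 14.3 does not say whether the looks use that response or the one after cycle 1, nor whether accrual pauses. If the looks use a different response, 73.9% is not the exact figure.

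**Conclusion.** The concern holds. With Table 5 applied as worded, power at an ORR of 75% is 73.9%: 6 points below the stated 80% and 7.4 points below the 81.2% of the single-stage test. The false-negative risk at the target is 26%. One-sided type I error is 4.0%, so error control is not in question.

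These figures assume that:

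- the boundaries are always obeyed;
- each look uses the final response of exactly the first 10, 20, 30, 40 and 50 patients;
- all 62 patients count in the denominator.

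**What to change.** **Required.** In section 14.2, say that with the futility rule of section 14.3 and success at 44 or more of 62, the design has 74% power at an ORR of 75% and a one-sided type I error of 4.0%. State that the futility rule is binding and which response assessment the looks use, because the 74% depends on both.

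Add a probability-of-success column to Table 6 and rerun the table at 62 patients. Its present averages at ORRs of 0.80, 0.75 and 0.60 (57.5, 53.0 and 26.9) correspond to a maximum of 60, so a 44/62 column beside them would mix two designs. At 62 the rows are:

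| True ORR | P(early stop) | Average patients | P(success) |
|---|---|---|---|
| 0.80 | 0.06 | 59.3 | 0.925 |
| 0.75 | 0.17 | 54.7 | 0.739 |
| 0.60 | 0.84 | 27.2 | 0.040 |
| 0.50 | 0.99 | 15.9 | 0.0005 |

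The cost is a sentence or two and a revised table. The stated power becomes less favourable.

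**Optional, if 80% is to be kept at 62 patients.** Look only after 30 and 50 patients, with the Table 5 boundaries of 18 and 32. Power is then 0.801 and type I error 0.047. Early stopping at an ORR of 60% drops from 0.84 to 0.79, and average enrolment there rises from 27 to 41. That is about 14 more patients treated when the combination adds nothing, and it needs a small amendment to the look schedule. This is a trade-off for the sponsor; correcting the stated power is needed either way.

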14.3 Futility Monitoring Rule

We expect the ORR of Rituximab + Acalabrutinib will be 15% or higher than Rituximab alone. We will monitor the ORR and stop the trial early for futility if observed ORR is unlikely to achieve the target (75%). A Bayesian method ³¹ will be used to monitor futility. The reference ORR was assumed to follow a Beta(60,40) distribution, which corresponds to an expected ORR of 60% with an effective sample size of 100. The prior distribution of true ORR was set as Beta(0.6,0.4), which also has an expected ORR of 60%, but with an effective sample size of 1. Futility monitoring will start from the 10th patient and in cohorts of 10 thereafter. We will stop the trial early if $\text{Pr}(\text{ORR} < 0.60 + 0.15 | \text{data}) > 0.9$, i.e. stop the trial early if the posterior probability of experimental ORR missing target (75%) is high (>0.9) given data. Table 5 summarizes early stopping boundaries, and table 6 summarizes operating characteristics.

Table 5. Summary of futility stopping boundaries using Bayesian monitoring rule. Futility monitoring will start from the 10th patient and in cohorts of 10. Trial will stop early if the number of CRs/PRs observed is less than or equal to the boundaries. For example, if we observed 5 or less CRs/PRs out of the first 10 patients, we will stop the trial early. Similarly, if we observed less than or equal to 12/20, 18/30, 25/40, or 32/50 CRs/PRs, we will stop the trial early for futility.

Total Number of Patients Treated	10	20	30	40	50
Number of CRs/PRs Observed <=	5	12	18	25	32

Table 6. Summary of operating characteristics based on 10,000 simulations using early stopping boundaries in table 5. E.g. If the true ORR is 75%, the early stopping probability is 0.17; if the true ORR is 60% (same as Rituximab alone), the early stopping probability is 0.84; if the true ORR is 50% (worse than Rituximab alone), the trial will stop early with probability 0.99. MultcLean v2.1 from MDACC was used to calculate the stopping boundaries and operation characteristics

Scenario	True ORR	Pr(Early Stopping)	Average #Patients Enrolled	Average #CR/PR Observed
1	0.80	0.06	57.5	46.0
2	0.75	0.17	53.0	39.8
3	0.60	0.84	26.9	16.1
4	0.50	0.99	15.9	7.9

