3.2 Number of Subjects

We plan to enroll 62 patients.

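### Section 14.3's printed futility formula (fixed 75% target) does not give Table 5's boundaries at 30, 40 and 50 patients, and Table 6's averages fit a maximum of 60 patients, not 62

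*Combined protocol and SAP*

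**What the plan says.** Section 14.3 describes the Bayesian futility rule in three ways.

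- **The model.** "The reference ORR was assumed to follow a Beta(60,40) distribution"; its mean is 60% and its effective sample size is 100. The experimental response rate has a Beta(0.6,0.4) prior, and the improvement sought is 15 percentage points.
- **The formula.** Stop if Pr(ORR < 0.60 + 0.15 | data) > 0.9, explained as "i.e. stop the trial early if the posterior probability of experimental ORR missing target (75%) is high (>0.9) given data".
- **The counts.** Table 5 lists boundaries of 5, 12, 18, 25 and 32 responders at 10, 20, 30, 40 and 50 patients. Its caption gives 5 of 10 as an example and then says "if we observed less than or equal to 12/20, 18/30, 25/40, or 32/50 CRs/PRs, we will stop the trial early for futility".

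Table 6 is headed "Summary of operating characteristics based on 10,000 simulations using early stopping boundaries in table 5" and does not state the maximum sample size used. Section 3.2 says "We plan to enroll 62 patients", and Section 14.2 says "The trial will be considered a success if 44 or more CRs/PRs are observed out of 62 patients".

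**The concern.** The formula and its explanation compare the experimental response rate with a fixed 75%. The reference distribution enters only through its mean, so its effective sample size of 100 plays no part. If the table was built with the full Beta(60,40) distribution, the formula and the table are different rules. A stop-or-continue rule has to give one answer for every possible count. A statistician recomputing the boundary from the formula at an interim look could recommend stopping where the table says to go on.

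Table 6 raises a separate question. Its averages look low for a 62-patient trial when the regimen works. Those averages are what the design reports about expected enrolment and responders.

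**Working it through.** **Inputs.** All are from Section 14.3 unless noted: prior Beta(0.6,0.4); reference Beta(60,40); margin 0.15; cutoff 0.9; looks at 10, 20, 30, 40 and 50; 10,000 simulations; planned size 62 (Sections 3.2 and 14.2); success at 44/62 (Section 14.2).

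**Step 1: boundaries.** After r responders in n patients the posterior is Beta(0.6 + r, 0.4 + n − r). Let F be its distribution function.

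- Fixed rule (the printed formula): P = F(0.75).
- Reference rule: P = ∫ F(x + 0.15) f(x) dx, where f is the Beta(60,40) density.

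The boundary is the largest r with P > 0.9. At 19/30, for example, the posterior is Beta(19.6, 11.4). The fixed rule gives 0.920 (stop) and the reference rule gives 0.885 (continue).

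| r/n | Fixed 75% | Beta(60,40) reference | Table 5 |
|---|---|---|---|
| 5/10 | 0.953 | 0.943 | stop |
| 6/10 | 0.847 | 0.835 | continue |
| 12/20 | 0.928 | 0.904 | stop |
| 13/20 | 0.838 | 0.813 | continue |
| 18/30 | 0.963 | 0.937 | stop |
| **19/30** | **0.920** | **0.885** | **continue** |
| 20/30 | 0.844 | 0.809 | continue |
| 25/40 | 0.959 | 0.922 | stop |
| **26/40** | **0.919** | **0.874** | **continue** |
| 27/40 | 0.855 | 0.808 | continue |
| 32/50 | 0.957 | 0.911 | stop |
| **33/50** | **0.921** | **0.867** | **continue** |
| 34/50 | 0.866 | 0.810 | continue |

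The reference rule reproduces Table 5 exactly: 5/12/18/25/32. The fixed rule gives 5/12/19/26/33. No fixed-target variant tried recovers Table 5:

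- Priors Beta(1,1), Beta(0.5,0.5), Beta(0.75,0.25) and Beta(1.5,0.5) at cutoff 0.9 all still give 19, 26 and 33.
- Prior Beta(6,4) at cutoff 0.9 gives 6/13/20/27/34.
- The stated prior at cutoff 0.95 gives 5/11/18/25/32, which misses 12/20.

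**Step 2: consequences.** These are exact binomial calculations across the five looks with a maximum of 62. The differing-count column is the chance of a first arrival at 19/30, 26/40 or 33/50 while the trial is still open under Table 5.

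| True ORR | Differing count reached | Early stop, Table 5 | Early stop, formula | Reaches 44/62, Table 5 | Reaches 44/62, formula |
|---|---|---|---|---|---|
| 0.80 | 0.015 | 0.058 | 0.071 | 0.925 | 0.917 |
| 0.75 | 0.058 | 0.173 | 0.218 | 0.739 | 0.720 |
| 0.60 | 0.132 | 0.844 | 0.897 | 0.040 | 0.037 |
| 0.50 | 0.035 | 0.990 | 0.996 | 0.0005 | 0.0005 |

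By look (30, 40, 50), the differing-count chance is 0.027 + 0.018 + 0.013 = 0.058 at ORR 0.75. At 0.60 it is 0.067 + 0.040 + 0.025 = 0.132 (0.1315 before rounding). The Table 5 early-stopping column agrees with Table 6's 0.06, 0.17, 0.84 and 0.99.

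**Step 3: the sample size behind Table 6.** Average patients / average responders, exact, with Table 5's boundaries:

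| True ORR | Table 6 | Maximum 60 | Maximum 62 |
|---|---|---|---|
| 0.80 | 57.5 / 46.0 | 57.5 / 46.0 | 59.3 / 47.5 |
| 0.75 | 53.0 / 39.8 | 53.0 / 39.8 | 54.7 / 41.0 |
| 0.60 | 26.9 / 16.1 | 26.9 / 16.1 | 27.2 / 16.3 |
| 0.50 | 15.9 / 7.9 | 15.9 / 7.9 | 15.9 / 8.0 |

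The simulation error of average patients is the standard deviation of the stopping size divided by √10,000. For a maximum of 62 it is about 0.11 at ORR 0.80 and 0.17 at 0.75. The stated values therefore lie (59.34 − 57.5)/0.109 ≈ 17 and (54.69 − 53.0)/0.167 ≈ 10 standard errors below the 62-patient values. At 0.60 and 0.50 the two sizes cannot be told apart. Early-stopping probabilities are the same for both sizes because the last look is at 50.

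**The case against.** The best defence is that Table 5 is the working rule. Its counts appear in the table and again in the caption, the caption tells the reader to stop at or below them, and Table 6 is said to use them. A team following the protocol would compare its count with the table. Beta(60,40) would have no purpose under a fixed target, so the formula can be read as shorthand that puts in the reference mean. The net effect is also small: the chance of reaching 44/62 differs by 1.9 percentage points at ORR 0.75 and 0.3 at 0.60. Some trials that the formula would stop at a differing count would stop later under Table 5 anyway. The 60-versus-62 point touches only descriptive averages.

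Most of this stands. It shows which rule was probably intended, and that nothing changes if Table 5 is followed. It does not remove the contradiction. The decision sentence is attached to the formula, the explanatory clause names a fixed 75% outright, and Table 5 is introduced only as a summary of the boundaries. Nothing says which prevails at a differing count.

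**Conclusion.** The concern holds on both parts. The printed formula and Table 5 are different rules and give opposite decisions at 19/30, 26/40 and 33/50. None of these is a rounding tie: the fixed-target probabilities are about 0.92 and the reference-based ones 0.87 to 0.89, against a cutoff of 0.9. Following the formula would raise early stopping by 4.6 percentage points at ORR 0.75 and 5.3 at 0.60. If Table 5 is followed, its boundaries and stopping probabilities are sound.

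Table 6's averages understate the planned trial by about 1.8 and 1.7 patients, and 1.5 and 1.2 responders, at ORR 0.80 and 0.75. That the simulations used 60 is an inference, since the table states no maximum, but simulation noise cannot explain the gap.

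These results assume the stated priors, looks only at 10 to 50 as Table 5 lists, and independent responses with a constant rate. This should be corrected, but it does not undermine the design.

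**What to change.** Replace the formula and its explanatory clause in Section 14.3 with: stop if Pr(ORR_E < ORR_ref + 0.15 | data) > 0.9, where ORR_ref ~ Beta(60,40) and ORR_E has prior Beta(0.6,0.4); the counts in Table 5 govern. Rerun Table 6 with a maximum of 62 patients and state that maximum in its caption.

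If a fixed 75% target was really intended, keep the formula, change Table 5 and its caption to 5/12/19/26/33, and rerun Table 6 with those boundaries at 62. The stated inputs favour the first route because they reproduce Table 5 exactly.

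The cost is one formula, one sentence and one rerun table. No extra patients are needed.

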14.4 Toxicity Monitoring

Toxicity is defined as any grade 4 adverse event or treatment related death. We will do interim looks for toxicity after every 15 patients have been treated and assessed for toxicity. If the estimated toxicity rate is higher than 20%, we will pause the study and a comprehensive safety assessment will be performed.

